16.3 Analysis of process data

The analysis of qualitative process evaluation data (interviews with participants and facilitators and recordings of participant-provider contacts) will be led by [name]. The data will be analysed using thematic analysis techniques⁴⁸ to elicit individual narratives and common themes relating to the qualitative research aims of the study (in particular to assess the feasibility and acceptability of the interventions and barriers to participation). Techniques to enhance objectivity and depth of analysis will include second coding of a sample of interviews (10%), negative case seeking /analysis, participant feedback and triangulation (both within the data and against other data from the study (e.g. outcomes data, other process measures). Discussion with our service user advisory group will help to ensure the relevance, credibility and trustworthiness of emergent themes. Data from facilitator contact sheets will be thematically summarised in the final study report and used to inform the refinements to the intervention and to the facilitator training materials. Qualitative analysis software (N-VIVO version 10 or above) will be used to organise and code the data. See Section 22.4 for details of data protection and confidentiality.

Satisfaction questionnaires will be scored and summarised using descriptive statistics (means, 95% confidence intervals). Intervention fidelity scores will be summarised in the same way and collated both in total and by facilitator. Where items are scored low for some or all facilitators, this will identify areas where change is needed (either via formative feedback and a training update or via changes to the intervention materials). The checklist scores and notes taken about good practice and learning needs during the review of the recordings will provide ideas for individualised formative feedback to

each facilitator (in written form). Examples of good practice will be flagged, transcribed and extracted as audio or audio-visual clips (with the facilitator's permission) to inform future training. The methodology has been used successfully before in previous complex intervention trials undertaken by the applicants^{42, 43}.

16.4 Revising the intervention and training materials

The results of the satisfaction questionnaires and contact report forms, as well as intervention fidelity checking and qualitative analyses will be used to revise the SkiM intervention and training materials. This work will be conducted after each cohort has completed the intervention. A four-month period between cohorts will allow data to be analysed, the intervention to be refined, documentary changes to be made and facilitators to be briefed so that the amended intervention can be assessed in the second cohort. Any further refinements will be made after the second cohort, so that a final version is available to be taken forward to a trial if appropriate.

17 ECONOMIC EVALUATION AND ANALYSES

The health economic evaluation is advised by [name], University of Exeter Medical School. A future fully-powered randomised controlled trial will include an economic evaluation, the aim of which will be to estimate the incremental cost-effectiveness of the SkiM intervention plus usual care vs. usual care alone, from an NHS and personal social services perspective (with other perspectives to be considered in sensitivity analyses). In such future analyses, cost-effectiveness will be assessed through the calculation of incremental cost-effectiveness ratios (ICER), estimating the incremental cost per unit of outcome, including health-related quality of life (i.e. cost per quality-adjusted life-years). Such analyses are not appropriate within this feasibility study, but we will assess

- (i) the feasibility and acceptability of collecting data on participant NHS, social services and related resource use via a self-report form,
- (ii) the feasibility and acceptability of collecting health outcome data relevant for the economic endpoints,
- (iii) the collection of resource data and estimation of related costs associated with delivery of the SkiM intervention (e.g. through facilitator contact sheets and interviewing management staff).

As part of the study, we will also develop the framework for the estimation of cost-effectiveness in analyses alongside any future full RCT, including plans for within-trial analyses and plans to extrapolate beyond trial outcomes using evidence synthesis and economic modelling methods to predict future outcomes (e.g. health events avoided due to any potential improvements in weight management /status).

18 END OF STUDY

The study will end on completion of data collection for the last participant for whom data is collected at the 18 month follow up.

REC Ref: 15/SW/0126

SkiM study protocol v8 – 29.03.16

19 **DISSEMINATION**

We will write up and publish the results of the study in a series of articles in peer-reviewed journals, aiming to place at least the main study report in an open access journal, in line with NIHR Open Access policy.

Over time, we aim to construct a web-based repository of weight loss maintenance intervention evidence, intervention materials, training materials and delivery strategies. We hope that this will be hosted by an authoritative national body (e.g. Association for the Study of Obesity, or the NHS Health Checks Resources website). Other dissemination activities will include conferences, publications and seminars for NHS staff /trainers involved in implementing NHS Health Checks or NICE guidance on diabetes prevention.

20 DISCONTINUATION / WITHDRAWAL

Participants are free to withdraw from the study at any time, and this will be emphasised during the consent process. If a participant chooses to withdraw he /she will be invited to provide reasons, which will be noted. To minimise dropout due to perceived measurement or intervention-attendance burden, they will be asked if they are willing to provide minimal data (weight-only) at follow-up, even if they do not wish to be involved in other study activities. Participants do not have to provide a reason for withdrawal and this will be reiterated by the PI (or authorised delegate) in the event that a participant withdraws. Anonymised data collected on participants prior to withdrawal will be retained for analysis unless the participant requests otherwise (and this will be stated on the consent form).

21 SAFETY REPORTING

The risks of harm associated with study procedures and the intervention are considered to be very low. Nevertheless, procedures are in place in case any should occur.

21.1 Definitions

Adverse Event (AE)

Any untoward medical occurrence, unintended disease or injury or any untoward clinical signs (including an abnormal laboratory finding) in subjects, users or other persons whether or not related to any research procedures or to the intervention.

Non-serious adverse events (see definition below) which are not related to study procedures or to the intervention will **not** be reported in this study.

Adverse Reaction (AR)

An adverse event judged as having a reasonable causal relationship to the intervention or to study procedures will be considered an Adverse Reaction (AR). The existence of a 'reasonable causal relationship' will be judged by the researcher reporting the event. Any evidence or argument to suggest a causal relationship will also be reported.

In this study, adverse reactions will be reported, regardless of seriousness.

Seriousness

Any adverse event or adverse reaction will be regarded as serious if it:

- i. results in death;
- ii. is life threatening;
- iii. requires hospitalisation or prolongation of existing hospitalisation;
- iv. results in persistent or significant disability or incapacity
- v. results in a congenital anomaly or birth defect; or
- vi. results in any other condition, judged to be significant by a clinician.

An adverse event meeting any one of these criteria will be a **Serious Adverse Event (SAE)**. An adverse reaction meeting any one of these criteria will be a **Serious Adverse Reaction (SAR)**.

In this study, all serious events will be reported whether they are related to the administration of the research procedures or not. A tabulated summary of reportable events is given in

Table 1:

Table 1: Reporting of Adverse Events

Event type	Reported by	Reported to	Timeframe
Adverse Reaction	CI or authorised	Chief investigator	Within 3 days*
	delegate	(CI), Sponsor	
Serious Adverse Event (SAE)	CI or authorised	CI, Sponsor	Within 24
	delegate		hours*
Serious Adverse Reaction (SAR)	CI or authorised	CI, Sponsor	Within 24
	delegate		hours*

^{*}of the CI (or authorised delegate) becoming aware of the event

Non-serious, unrelated AEs will not be recorded

21.2 Reporting adverse events to Investigator and Sponsor

Non-serious adverse events which are unrelated to the intervention or study procedures will not be recorded or reported. Adverse events which are serious and/or related to study procedures or the SkiM intervention, from the point that informed consent is obtained until the end of the study, will be recorded in the case report form (CRF) and reported as described below.

The method for collecting adverse event information will be a) via the data collection visits at follow-up assessments, and b) direct contact from participants or intervention facilitators.

21.2.1 Reporting non-serious events

The CI (or authorised delegate) will question participants about adverse events at the 6 and 12 month data collection visits and will be responsible for adjudging relationship to the intervention and study

procedures. Related adverse events will be documented in the purpose-designed CRF. Multiple symptoms will be recorded as separate events. The events will be reported to the CI and Sponsor on a designated report form which will capture the relatedness of the event to study procedures/the intervention, in the opinion of the PI (or authorised delegate).

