12 FOLLOW-UP DATA COLLECTION (AT 6, 12 AND 18 MONTHS)

Two weeks prior to follow-up visits at 6 and 12 months post baseline, questionnaires and accelerometers will be posted to participants by CTU with instructions for their use and a request to complete the questionnaires and wear the accelerometer for 7 days before the visit. At the meeting the researcher will

REC Ref: 15/SW/0126

• Go through the questionnaire booklet to ensure all questions have been answered

- Check information provided by the participant regarding healthcare service utilisation over the preceding period
- Collect the accelerometer.

In addition, participants will be asked to identify any newly diagnosed conditions or new medications started during the intervention delivery periods, as well as any other management services or interventions used (including commercial weight loss programmes) and any smoking cessation attempts (which can cause substantial weight gain).

At the 18-month assessment, the only quantitative measurements will be weight and waist circumference. See Appendix 2 for the full schedule of quantitative measurements.

Participant travel expenses will be paid for attending, if needed, and those without transport or convenient public transport will be reimbursed for use of a taxi to and from the meeting venue.

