14.3.1 Outcome measures

The primary outcome in a trial of weight loss maintenance strategies will be change in body weight (kg) between 6 month and 18 or 24 month follow ups, i.e. after a period of weight loss.

Proposed secondary outcome measures for a trial are:

- Changes in minutes of moderate activity per week and total energy expenditure (assessed by accelerometer)
- Body Mass Index (BMI)
- Waist circumference
- Self-reported quality of life (EQ-5D-5L ³⁹)

In addition, data will be collected on any newly diagnosed medical conditions or changes in medication during the study period, as well as any other weight management services or interventions used (cointerventions), and smoking cessation attempts (which can cause substantial weight gain).

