32 APPENDICES

Appendix 1 - Study Gantt Chart

Appendix 2 – Schedule of measurements

	Assessment visit 1 (Baseline*)	Assessment visit 2 (6 months)	Assessment visit 3 (12 months)	Assessment visit 4 (18 months)
Demographics (incl. age, sex, socio-economic status)	X			
Medical history (incl weight changes and management, and co-morbidities)	х			
Changes in health status		Х	Х	Х
Depression & Anxiety (screening questions then Hospital Anxiety & Depression Scale if indicated)	Х			
Body measurements (Weight, height, waist circumference)	X			
Body measurements (Weight, waist circumference)		х	X	X
Physical activity levels (7 day accelerometry)	X	х	X	
EQ5D-5L	X	Х	Х	
Health & Social Care Use Inventory (including medication)	X	х	X	X
Self-reported Habit Index (Automaticity)	Х	Х	Х	
Self-efficacy (Lapse management)	Х	Х	X	
Self-efficacy (Managing external influences)	Х	Х	X	
Perceived maintenance tension	Х	Х	Х	
Maintenance resilience questionnaire	Х	Х	Х	
Weight-related identity beliefs	Х	Х	Х	
Adverse events		Х	X	

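### Adverse events are to be recorded to the end of the study at 18 months, but participants are scheduled to be asked about them only at 6 and 12 months

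*Protocol*

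**What the plan says.** Section 21.2 sets the recording window for events that are serious, related, or both: "from the point that informed consent is obtained until the end of the study, will be recorded in the case report form". Section 18 fixes the end: the study closes when, for the last participant, "data is collected at the 18 month follow up". Section 21.2 gives two collection routes without ranking them: the follow-up assessment visits, and direct contact from participants or facilitators. It names no months, but the heading of section 12 defines follow-up as 6, 12 and 18 months.

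The questioning itself is scheduled in two places. Section 21.2.1 states that the chief investigator or a delegate "will question participants about adverse events at the 6 and 12 month data collection visits". In Appendix 2 the row labelled "Adverse events" is marked at visits 2 and 3 (6 and 12 months) and blank at visit 4 (18 months).

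The content of the 18-month visit is described in different ways. Section 12 says: "At the 18-month assessment, the only quantitative measurements will be weight and waist circumference". Appendix 2 also marks change in health status and the health and social care use inventory at 18 months. For new diagnoses and medications, section 12 asks about "any newly diagnosed conditions or new medications started during the intervention delivery periods", while section 14.3.1 says that data will be collected on "any newly diagnosed medical conditions or changes in medication during the study period".

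**The concern.** The plan commits to a recording window that its own visit schedule does not serve. Section 21.1 requires every serious event to be reported whether or not it is related, so the duty does not lapse when the programme ends. Relatedness of serious events is adjudicated only after they have been recorded (section 21.2.2), so an event that nobody asks about and nobody volunteers is never adjudicated.

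The first stopping condition in section 16.2.1 turns on serious events attributable to the intervention or the study procedures. Incomplete ascertainment late in follow-up weakens the information behind that decision, and the study is meant to rehearse the procedures of the future trial.

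**Working it through.** The plan states no figure to reproduce. The check compares the passages and takes one ratio.

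**Inputs**
- Recording window: consent to end of study (section 21.2).
- End of study: last 18-month data collection (section 18).
- Assessments: baseline, 6, 12 and 18 months (section 7.1).
- Last scheduled adverse-event question: 12 months (section 21.2.1 and Appendix 2).
- Length of involvement: 18 to 20 months (section 13).
- Intervention period: 6 months (section 7.1).

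**Share of follow-up after the last scheduled question** = (length − 12) / length
- At 18 months: (18 − 12)/18 = 6/18 = 33.3%.
- At 20 months: (20 − 12)/20 = 8/20 = 40.0%. This is an upper bound, because it holds the 12-month visit on time while the last visit runs late.
- With a question added at 18 months, on 18 months of follow-up: 0/18 = 0%.

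**Is questioning about serious events scheduled elsewhere?** Section 21.2.1 is headed for non-serious events, so it might not govern serious ones. But section 21.2.2 covers recording, adjudication and onward reporting and sets no time for asking participants. The Appendix 2 row makes no distinction by seriousness. The only support for 18 months is indirect: section 21.2 refers to follow-up assessments, and section 12 counts 18 months among them.

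**What remains after month 12?**
- Spontaneous contact. Facilitators are one named source, but delivery lasts 6 months, so their regular contact has ended by then.
- Qualitative interviews at 18 months with 12 to 15 participants per arm (section 15.2). Over two arms this is 24 to 30 people: 24/80 = 30% to 30/80 = 37.5% of the 80 in section 16.2, or 24/110 = 22% to 30/110 = 27% of the 110 in the study summary.
- The Appendix 2 row on change in health status. It is not clearly a quantitative measurement, so it need not conflict with section 12. If it is asked with the recall period in section 12, however, it covers the delivery period and not months 12 to 18.
- The Appendix 2 service-use inventory. It could reveal a hospital admission, but section 12 leaves no room for it at 18 months.

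Neither of the last two rows is linked to adverse-event reporting.

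**Is the 18-month visit carried through elsewhere?** Not consistently. Section 14.3.2 puts all participant outcomes at 0, 6 and 12 months. Section 13 calls the visit at 18 to 20 months the second follow-up visit. The timetable in the study summary lists an 18-month assessment only for Phase 2.

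**The case against.** The strongest reply is that ascertainment does not stop at month 12. Health status and service use are marked at 18 months, hospital admission is itself a seriousness criterion, interviews continue in a subsample, and spontaneous reporting stays open. The stopping condition also counts events that emerge from the qualitative data. Section 21.2.2 refers to a separate operating procedure for adverse-event reporting, which is not shown and may say more. The protocol rates the risk as very low (section 21), and the gap begins six months after delivery ends. All of this stands, and it limits the weight of the point. It does not remove the mismatch between the window and the schedule.

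A reader might infer more than the documents support:
- *That events in months 12 to 18 would be missed.* The routes above remain, so the most that can be said is that some may be.
- *That up to one third of reportable events are affected.* This needs a constant event rate. Non-serious events are reportable only if related, delivery ends at 6 months, and accelerometry and the process questionnaires end at 12 months. Related events should therefore fall mostly earlier. A constant rate is plausible only for unrelated serious events, which do not bear on the stopping condition.
- *That the 18-month weight cannot be interpreted.* Outcomes here serve to test collection and completion (section 14.3), and no formal comparison between arms is planned (section 16.1).
- *That everyone is seen at 18 months.* The timetable lists that assessment only for Phase 2, and section 16.2 assumes incomplete follow-up.

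**Conclusion.** The inconsistency is real. Two places limit adverse-event questioning to 6 and 12 months, against a window that runs to the 18-month end of study, so a single slip of the pen is an unlikely explanation. Followed as written, the plan leaves 6 of 18 months (33%, at most 40% on a 20-month involvement) without a scheduled adverse-event question. That share describes time, not events.

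Serious events in this period may be under-ascertained; the documents do not allow an estimate of how many. The point is minor to moderate. This rests on delivery ending at 6 months, on the protocol's own view that the risk is very low, and on the partial routes that remain. The differences over 18-month content and recall period matter here mainly because they decide whether those partial routes work.

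**What to change.** - Appendix 2: mark adverse events at visit 4 (18 months).
- Section 21.2.1: change the visits to 6, 12 and 18 months wherever an 18-month visit takes place, and make clear that the question covers serious events too.
- Section 12: list the 18-month content so that it agrees with Appendix 2, in particular on the service-use inventory.
- Sections 12 and 14.3.1: use one recall period for new conditions and medications. Asking at each visit about the time since the last assessment would cover the study period.
- Study summary timetable: state whether Phase 1 has an 18-month visit, so that it is clear to whom the added question applies.

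Ending the recording window at 12 months would also remove the mismatch, but by shortening safety capture when a later visit is already planned. Adding the question costs a few minutes at that visit, a small change to the case report form and a minor amendment.

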21.2.2 Reporting serious adverse events

Serious adverse events will be recorded and sent for subsequent adjudication by two clinical advisors ([name] of St Leonards Practice and [name] of Witheridge Medical Centre). If one advisor is not available, [name] (academic GP and head of the primary care research group at UEMS) will be consulted instead. The role of the adjudicators will be to judge whether the event is likely to be due to participation in the study.

Onward reporting: Reporting of all SAEs will follow a study-specific SOP (Standard Operating Procedure) for Adverse Event Reporting. Briefly, all SAEs that are related to the study or intervention procedures will be reported to NHS Research Ethics Committee using the non-CTIMP Safety Report Form within 15 days of the CI becoming aware of the event.

If incomplete information is available to the CI (or authorised delegate) at the time of when s/he becomes aware of a reportable event, all information available at that time should be reported onward as soon as possible. The CI will coordinate adverse event information, including generating requests for missing/additional information as required. Any documentation will be anonymised before passing on for adjudication /reporting purposes.

All reportable events will be followed until resolution where possible or until the end of the data collection period.

21.3 Processing safety information

Safety information in the form of designated adverse event report forms, with any relevant documents, will be sent to the clinical advisors for adjudication of whether they might be related to study participation or not. Summary reports listing all reportable adverse events and adjudication about relatedness (and the rationale for these decisions) will be compiled by the CI and sent to the Sponsor on a case by case basis. Events which are both serious and related to the SkiM intervention or study procedures will be communicated immediately to the CI who will be required to decide if such an event is unexpected.

If unexpected, the event will be regarded as an Unexpected Serious Adverse Reaction and will be reported to the Research Ethics Committee by the CI within **15 days** of the CI (or authorised delegate) becoming aware of the event, using the SAE report form for research other than clinical trials of investigational medicinal products (non-CTIMPs) published on the NRES website. The report will be copied to the Sponsor.

REC Ref: 15/SW/0126

SkiM study protocol v8 - 29.03.16

